11.2 Data Analysis

Primary outcome: Failure is counted when a patient experiences any hospital episode related to treatment for atrial arrhythmia. Patients are censored from their treatment group when they switch to a treatment other than that to which they were originally assigned or when they leave their treatment group without having experienced a hospital episode.

Data will be analyzed using the intention-to-treat principle and a p value of 0.05 or less will be considered significant. Primary outcome will be analysed using Kaplan-Meier statistics and differences will be tested using log-rank test and proportional hazards models. Other outcomes will be compared using t-test for continuous and Chi-square test or Fisher exact test for categorical variables and the appropriate generalized linear model will be used.

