8.3 Crossover between therapies

Following the week 12 visit, a patient from any group, the Investigator may initiate further drug therapy or schedule a standard ablation procedure for the patient. However, the following are required;

- i) *Ablation Arms (Conventional and AVATAR-AF):* Can start anti-arrhythmic drugs or further redo-ablation if there is ECG/Holter documentation of recurrent AF/AT
- ii) *Drug Therapy Arm:* May receive ablation therapy if failed one anti-arrhythmic at maximum standard dose or two anti-arrhythmic agents at sub-maximal dose or due to side effects.
- iii) *New tachycardia documented that needs treatment (VT/AVNRT/AVRT).* The patient is withdrawn from the study

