13.2 Consent

Consent to enter the study must be sought from each participant only after a full explanation has been given, an information sheet offered and time allowed for consideration. Signed participant consent must be obtained. The right of the participant to refuse to participate without giving reasons must be respected. After the participant has entered the study the clinician remains free to give alternative treatment to that specified in the protocol at any stage if he/she feels it is in the participant's best interest, but the reasons for doing so must be recorded. In these cases, the participants remain in the study for the purposes of follow-up and data analysis. All participants are free to withdraw at any time from the protocol treatment without giving reasons and without prejudicing further treatment.

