5.7. Randomisation

Eligible patients who have given written, informed consent and who meet all the inclusion criteria and no exclusion criteria will undergo 1:1:1 randomisation to an un-blinded treatment of either AVATAR-protocol AF Ablation, medical anti-arrhythmic therapy or conventional AF ablation. Randomisation will be performed electronically using the InForm electronic data capture system and will be stratified by site.

From the date of randomisation, the 1st Intervention date (ablation or anti-arrhythmic medication change) must occur 28 days \pm 7days after this, therefore an ablation procedure date will be identified according to local EP catheter lab availability for each consenting, eligible

patient and randomisation of the patient will then be scheduled for 28 days \pm 7 days from this available date.

The patient may be withdrawn from any AF ablation treatment by the Investigator if any safety concerns arise during the period between randomisation and the ablation which make the patient an unsuitable candidate for the procedure. The patient will then be withdrawn from the study.

6. Analysis Set

All treatment evaluation will be performed on the principle of intention to treat (ITT) with additional per-protocol analyses ran alongside if defined (see Section 8). The per-protocol analysis set will consist of patients who received treatment originally allocated.

A sensitivity analysis will also be performed excluding patients who are withdrawn from the study between randomisation and start of treatment / 1st intervention. Any subjects that have withdrawn during this period will still be required to attend the end-of-study follow-up visit.

7. Variables of Analysis

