8.2. Primary Endpoint Analysis

Failure is counted when a patient experiences any hospital episode related to treatment for atrial arrhythmia. Time to failure will be taken as the time from 1st Intervention to the time of event.

Data will be analysed using the intention-to-treat principle and a p-value of 0.025 or less will be considered significant. Primary outcome will be analysed using Kaplan-Meier statistics and differences between treatment arms will be assessed using log-rank testing and proportional hazards models. Models containing one or more of the following covariates may also be assessed if deemed necessary; site, weight, hypertension, number of anti-arrhythmic taken by patient prior to 1st intervention.

Primary endpoint analysis will be carried out between AVATAR-AF Ablation and the Anti-Arrhythmic drug treatment arm in order to investigate the primary objective. The secondary objective will be assessed by testing AVATAR-AF Ablation against the Conventional Ablation arm.

An additional per-protocol analysis will be carried out in conjunction with the above.

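### Protocol 11.2 censors patients at a treatment switch while claiming intention to treat; the SAP drops that rule and puts no censoring rule in its place

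*Protocol*

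**What the plan says.** Protocol 11.2 defines failure on the primary outcome as any hospital episode for treatment of atrial arrhythmia. It then adds: "Patients are censored from their treatment group when they switch to a treatment other than that to which they were originally assigned". The same sentence also censors patients who leave their group event-free. The next paragraph opens: "Data will be analyzed using the intention-to-treat principle".

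Other parts of the protocol bear on this:

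- Section 8.3 permits crossover in every arm after the week 12 visit: "the Investigator may initiate further drug therapy or schedule a standard ablation procedure for the patient". The conditions are documented recurrence in the ablation arms, and drug failure or side effects in the drug arm.
- Section 13.2 adds that "the clinician remains free to give alternative treatment to that specified in the protocol at any stage", and says of such patients: "In these cases, the participants remain in the study for the purposes of follow-up and data analysis".
- Section 14.3.2 asks for follow-up to study end even after an endpoint, because all patients are in the intention-to-treat analysis.

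SAP 8.2 repeats the failure definition ("Failure is counted when a patient experiences any hospital episode related to treatment for atrial arrhythmia") and states: "Data will be analysed using the intention-to-treat principle and a p-value of 0.025 or less will be considered significant". SAP section 6 applies intention to treat to every treatment comparison, with a per-protocol set of patients who received their allocated treatment. No SAP section says when or why a patient is censored.

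**The concern.** Two problems follow. First, Protocol 11.2 contradicts itself: a result censored at switch is an on-treatment result and could not be reported as intention to treat. Second, the protocol removes episodes after a switch, whereas the SAP's intention-to-treat statement with an unrestricted event definition would ordinarily include them. Two analysts, each following one document, could analyse different event sets.

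The log-rank test and the Cox model assume that censoring is unrelated to prognosis. A patient who switches because the arrhythmia has recurred or the drug has failed is likely to be at raised risk of the very episode being counted. If such switches come before a counted episode and are more common in one arm, the hazard ratio is biased: towards no effect if they are mainly in the drug arm, and in favour of AVATAR if they are mainly in the AVATAR arm.

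**Working it through.** **Inputs from the plan (Protocol 11.1, SAP 5.5).** 12-month proportions with an episode: 0.63 drug, 0.40 AVATAR, 0.20 conventional; 100 evaluable patients per arm; two-sided alpha 0.025; 103 events; stated power 0.80.

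**The plan's own figure.** Expected events: 100 × (0.63 + 0.40) = 103, as stated. Under proportional hazards, HR = ln(0.60)/ln(0.37) = 0.514.

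- Freedman: Φ(√103 × (1 − 0.514)/(1 + 0.514) − 2.241) = Φ(1.02) = 0.85.
- Schoenfeld: Φ(√(103/4) × |ln 0.514| − 2.241) = Φ(1.14) = 0.87. Simulation agrees (0.86–0.87).

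The stated 0.80 is not reproduced at alpha 0.025. That is a separate matter, but it means the baseline for the comparisons below is 0.87, not 0.80.

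**Closed-form check.** Suppose a fraction s of would-be drug-arm first episodes, at any stage, is censored by a switch just beforehand. Then HR = 0.514/(1 − s) and events = 100 × [0.63(1 − s) + 0.40]. With s = 0.05: HR 0.54, 99.85 events, Freedman power 0.77. With s = 0.10: HR 0.57, 96.7 events, power 0.67.

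**Simulation with switching after week 12.** Exponential event times matched to the plan's proportions; 100 per arm; follow-up to 12 months; Cox HR averaged on the log scale; log-rank at two-sided 0.025; 4,000 to 8,000 replicates per scenario. A share s of would-be events after week 12 is censored by an earlier switch. The ranges cover three timings of the switch: in the second half of the interval from week 12 to the event; at 50–100% of the event time, only if that falls after week 12; and at the later of week 12 and 50–100% of the event time.

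The number of patients involved can be checked by hand. Drug-arm events by week 12 are 1 − 0.37^(12/52) = 0.205, leaving 0.63 − 0.205 = 0.425 afterwards. So s = 10% censors at most about 4 patients per 100.

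AVATAR v drug, switching in the drug arm only:

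| s | HR | Power |
|---|---|---|
| 0 | 0.51 | 0.87 |
| 2–5% | 0.52–0.53 | 0.82–0.85 |
| 10% | 0.54–0.55 | 0.76–0.79 |
| 20% | 0.57–0.59 | 0.63–0.68 |
| 30% | 0.61–0.64 | 0.46–0.54 |

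Other cases:

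- Switching possible from day 0 (as 13.2 allows), s = 10%, drug arm only: HR 0.56, power about 0.71.
- Equal 20% shares in both arms: HR 0.51, power 0.81–0.83.
- Drug-arm switching unrelated to prognosis in 10–50% of patients: HR 0.51, power 0.83–0.86.
- No true difference (50% in each arm), 10/20/30% censored in AVATAR only: false rejection about 3%, 5–6% and 8–12%, against a nominal 2.5%. With equal shares it stays at 2–3%.

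AVATAR v conventional, switching in the AVATAR arm only:

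| s | HR | Power |
|---|---|---|
| 0 | 2.32 | 0.82 |
| 10% | 2.15–2.17 | 0.71–0.72 |
| 20% | 1.98–2.04 | 0.58–0.63 |
| 30% | 1.81–1.89 | 0.44–0.50 |

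With equal 20% shares in this comparison, HR is 2.33–2.34 and power 0.75–0.76.

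**The case against.** The strongest reply is that the design leaves little room for a switch before a counted episode. Drug changes at the week 4 and week 8 reviews, and the week 10 redo, belong to the assigned strategy. Failing to enter the discharge protocol at week 12 is itself a primary endpoint (Protocol 7.1.1, SAP 7.1). After that, no clinic visit is scheduled until month 12, so most crossovers would begin with a patient-requested visit that already counts. What remains is switches for side effects, at the clinician's discretion, or arranged without a counted visit, and switches that share a date with an endpoint. This stands as an argument about size. It is why the 2–5% row is shown, and why the larger rows should not drive the judgement.

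Second, the SAP never states that post-switch episodes count. That is correct: the disagreement between the documents is an inference from intention to treat and an unrestricted event definition. The contradiction inside Protocol 11.2 needs no inference.

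Third, a patient censored at a switch still contributes time at risk, so is arguably still in the analysis as 13.2 requires. This weakens the conflict with 13.2 but does not make the analysis intention to treat.

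Fourth, neither document defines a switch. It is unclear whether AVATAR's redo by conventional pulmonary vein isolation, or a change of drug agent, would trigger censoring. Whether a crossover ablation is itself a counted episode is also unclear, because the failure wording in 11.2 is wider than the endpoint in 8.1. Both gaps make the reach of the present rule harder to predict.

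**Conclusion.** The concern holds. A stated rule for the primary analysis is incompatible with the principle claimed in the next paragraph, and the SAP neither adopts nor replaces it. This should be fixed before analysis.

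The numerical effect is unknown because the documents give no switch rate. It is modest if few switches precede a counted episode, and the hazard ratio barely moves if switching is balanced or unrelated to prognosis. It becomes material for power, or for the false-positive rate, only if prognosis-related switching is concentrated in one arm and removes roughly 10% or more of later episodes. The simulated figures rest on exponential event times and assumed switch shares and timings; they are illustrations, not forecasts. The conclusion about labelling does not depend on them: a result censored at switch is not intention to treat at any switch rate.

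**What to change.** Delete the censoring sentence from Protocol 11.2. In its place, and in SAP 8.2, state that:

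- the primary analysis keeps each patient in the randomised arm and counts adjudicated episodes up to 12 months, whatever treatment is later received, including any redo;
- censoring occurs only at death, loss to follow-up, withdrawal from the study or 12 months;
- a week 12 discharge-protocol failure is an event even if its date coincides with a switch.

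Censoring at switch can be kept as a labelled sensitivity analysis, with a written definition of a switch and the number of switches before a counted episode reported by arm.

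This changes the analysis wording only; the crossover rules in 8.3 are untouched. It does not settle two neighbouring matters: investigator-led withdrawals under 5.4 and 8.3, and the starting time for patients withdrawn before the first intervention.

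The cost is one paragraph in each document, with Trial Steering Committee approval of the protocol amendment under 14.1. No new data collection is needed, since Protocol 7.2 already provides for telephone follow-up of all randomised patients to month 12.

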11 STATISTICAL ANALYSIS

11.1 Sample Size Calculation

In this time-to-event study of hospital episodes, required sample numbers have been estimated using the log-rank test under the Freedman method based on the occurrence of first event during the 12-month follow-up period. The null hypothesis is that there is no difference in the distributions. Adopting a conservative approach, an initial two-sided alpha of 0.05 is chosen, given the need to allow for the inherent multiple testing between the three arms of the study, the conservative Bonferroni correction is applied and the alpha value used in the power calculations is reduced to 0.025.

Estimating the proportion experiencing a hospital episode in the follow-up period in the anti-arrhythmic arm as 0.63 and the corresponding proportion in the AVATAR ablation arm as 0.40, assuming the occurrence of 103 events, with 100 evaluable patients in each of the two treatment arms yields a power of 0.8. A similar power is obtained for the comparison of the AVATAR ablation arm (0.40) and the conventional AF ablation arm (0.20).

A sensitivity analysis indicates that these sample size estimates are reasonable. It is anticipated that the loss to follow-up will be small, approximately 7%. Consequently, 321 patients will be randomised in a 1:1:1 manner to a treatment strategy of either AVATAR-protocol ablation, anti-arrhythmic therapy or conventional AF ablation and followed-up for 1 year.

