5.5. Sample Size

In this time-to-event study of hospital episodes, required sample numbers have been estimated using the log-rank test under the Freedman method based on the occurrence of first event during the 12-month follow-up period. The null hypothesis is that there is no difference in the distributions. Adopting a conservative approach, an initial two-sided alpha of 0.05 is chosen, given the need to allow for the inherent multiple testing between the three arms of the study, the conservative Bonferroni correction is applied and the alpha value used in the power calculations is reduced to 0.025.

Estimating the proportion experiencing a hospital episode in the follow-up period in the anti-arrhythmic arm as 0.63 and the corresponding proportion in the AVATAR ablation arm as 0.40, assuming the occurrence of 103 events, with 100 evaluable patients in each of the two treatment arms yields a power of 0.80. A similar power is obtained for the comparison of the AVATAR ablation arm (0.40) and the conventional AF ablation arm (0.20).

A sensitivity analysis indicates that these sample size estimates are reasonable. It is anticipated that the loss to follow-up will be small, approximately 7%. Consequently, 321 patients will be randomised in a 1:1:1 manner to a treatment strategy of either AVATAR protocol ablation, anti-arrhythmic therapy or conventional AF ablation and followed-up for 1 year.

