8.3. Secondary Endpoint Analysis

Time to death or stroke; time to procedural/drug-based complication and time to hospital episode resulting in change in therapy will be analysed using Kaplan-Meier statistics. Differences between treatment arms will be assessed using log-rank testing and proportional hazards models. Models containing one or more of the following co-variates may also be assessed if deemed necessary; site, weight, hypertension, number of anti-arrhythmic taken by patient prior to 1st intervention.

Secondary endpoint analysis will be carried out between AVATAR-AF Ablation and the Anti-Arrhythmic drug treatment arm in order to investigate the primary objective. The secondary objective will be assessed by testing AVATAR-AF Ablation against the Conventional Ablation arm.

Additional per-protocol analyses will be carried out in conjunction with the above.

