8.4. Safety Variable Analysis

Adverse events will be summarised by treatment and severity. A separate table summarising adverse events and their relationship to study treatment will also be produced.

Serious adverse events will be listed and summarised by site, category and treatment. A separate table summarising serious adverse events and their relationship to study treatment will also be produced.

All safety variables will be summarized in the form of frequency tables for categorical variables or descriptive statistics for continuous variables. Quality-of-Life (QoL) questionnaire results will be summarised by Health State Score. Atrial Fibrillation Effect on QualiTy-of-life (AFEQT) questionnaire results will be summarised by both overall AFEQT score and subscale score derived using the formulae stated within the AFEQT Questionnaire Instruction and Scoring Manual

REFERENCES

If it is deemed appropriate, treatment effect will be assessed via t-test for continuous variables and Chi-square test or Fisher exact test for categorical variables (with the appropriate generalized linear model being used). Models containing one or more of the following covariates may also be assessed if deemed necessary: site, weight, hypertension, number of anti-arrhythmics taken by patient prior to 1st intervention. A p-value of 0.025 or less will be considered significant. Any testing for treatment effect will be carried out between AVATAR-AF Ablation and the Anti-Arrhythmic drug treatment arm in order to investigate the primary objective. The secondary objective will be assessed by testing AVATAR-AF Ablation against the Conventional Ablation arm.

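### Protocol 11.2 tests at 0.05 and SAP 8.2 at 0.025, so a primary p-value between the two is positive under one document and negative under the other

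*Protocol*

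**What the plan says.** Protocol 11.2 gives the decision rule as "Data will be analyzed using the intention-to-treat principle and a p value of 0.05 or less will be considered significant". The sentence comes before both the primary analysis (Kaplan-Meier, log-rank, proportional hazards) and the tests for other outcomes, and sets no other threshold for either.

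Protocol 11.1 takes a different line. It begins with "an initial two-sided alpha of 0.05 is chosen", refers to multiple testing among the three arms, and then says "the conservative Bonferroni correction is applied and the alpha value used in the power calculations is reduced to 0.025". SAP 5.5 repeats this.

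SAP 8.2, on the same primary analysis, says "a p-value of 0.025 or less will be considered significant". It names two comparisons: AVATAR against anti-arrhythmic drugs for the primary objective, and then "The secondary objective will be assessed by testing AVATAR-AF Ablation against the Conventional Ablation arm".

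For other outcomes the SAP is uneven. Section 8.4 (safety variables) says "A p-value of 0.025 or less will be considered significant". Section 8.3 (secondary endpoints) says "Differences between treatment arms will be assessed using log-rank testing and proportional hazards models" and gives no threshold.

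On power for AVATAR v drugs, SAP 5.5 says "assuming the occurrence of 103 events, with 100 evaluable patients in each of the two treatment arms yields a power of 0.80"; protocol 11.1 gives the same figure.

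**The concern.** The rule for declaring the trial positive should be single and fixed before the data are seen. Here the two governing documents use almost the same sentence with different thresholds. A two-sided p-value above 0.025 and up to 0.05 is significant under protocol 11.2 and not significant under SAP 8.2.

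The protocol also undercuts itself. A Bonferroni correction that enters the power calculation but not the test gives no protection against false positives. If both AVATAR comparisons are tested at 0.05, the control described in 11.1 is lost.

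For the secondary endpoints, the 0.05 in protocol 11.2 is the only threshold stated. Correcting the primary threshold alone would leave that gap. Treatment is un-blinded, and SAP 8.6 allows interim primary-endpoint reports on request, so a threshold settled late would be hard to defend.

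**Working it through.** **Inputs.** From protocol 11.1 and SAP 5.5: event proportions 0.63 (drugs), 0.40 (AVATAR) and 0.20 (conventional); 100 evaluable patients per arm; 103 events for AVATAR v drugs; Freedman method for the log-rank test; two-sided alpha 0.025 after correction from 0.05. Normal quantiles: 1.960 for two-sided 0.05 and 2.241 for two-sided 0.025.

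**1. The plan's own figures.**
- Corrected alpha: 0.05 / 2 = 0.025. This reproduces and matches the two comparisons in SAP 8.2.
- Events, AVATAR v drugs: 100 × (0.63 + 0.40) = 103. This reproduces.
- Power of 0.80 at 0.025: this does not reproduce (step 2).

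**2. Power.** Freedman: power = Φ(√d × (1 − HR)/(1 + HR) − z), with HR = ln(1 − p₁)/ln(1 − p₂), where p₁ is the lower event proportion, p₂ the higher, and d the number of events.

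AVATAR v drugs:
- HR = ln(0.60)/ln(0.37) = 0.514, and (1 + HR)/(1 − HR) = 3.113.
- √103 / 3.113 = 3.260.
- At 0.025: Φ(3.260 − 2.241) = 0.846.
- At 0.05: Φ(3.260 − 1.960) = 0.903.
- The stated 0.80 fits an alpha of about 0.017, which gives 0.809.

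AVATAR v conventional:
- HR = ln(0.80)/ln(0.60) = 0.437, and the factor is 2.551.
- Events = 100 × (0.40 + 0.20) = 60, and √60 / 2.551 = 3.036.
- At 0.025: Φ(3.036 − 2.241) = 0.787, consistent with the plan's statement of similar power.
- At 0.05: Φ(3.036 − 1.960) = 0.859.

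**3. The disputed zone as an observed hazard ratio.** Critical HR ≈ exp(−2z/√d). At 103 events this is exp(−2 × 1.960/10.149) = 0.680 at 0.05 and exp(−2 × 2.241/10.149) = 0.643 at 0.025.

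**4. Chance of landing in the zone.** This is power at 0.05 minus power at 0.025.

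| Scenario | Power at 0.05 | Power at 0.025 | Difference |
|---|---|---|---|
| AVATAR v drugs, design effect | 0.903 | 0.846 | 0.057 |
| AVATAR v conventional, design effect | 0.859 | 0.787 | 0.072 |
| AVATAR v drugs, true HR 0.65 (assumed) | 0.576 | 0.465 | 0.112 |

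The HR of 0.65 is not in the documents. It is close to the worst case: the zone is 2.241 − 1.960 = 0.281 wide on the z scale, so its probability cannot exceed about 2Φ(0.141) − 1 = 0.112. Under the null it is 0.05 − 0.025 = 0.025.

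**5. Family-wise error over the two comparisons.** Two-sided, 1 − P(|Z₁| ≤ z and |Z₂| ≤ z), bivariate normal. The correlation is an assumption; 0.5 corresponds to a shared arm with equal allocation.

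| Correlation | 0.05 each | 0.025 each |
|---|---|---|
| 0 | 0.0975 | 0.0494 |
| 0.5 | 0.0907 | 0.0465 |
| 0.7 | 0.0835 | 0.0430 |
| Bonferroni bound | 0.10 | 0.05 |

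**The case against.** The best defence is that the intended rule is plain. SAP 8.2 and 8.4 both use 0.025, the SAP change history records a deliberate move to that value, and the 0.05 in protocol 11.2 looks like text that was not updated. By convention an analyst would follow the SAP, and the two rules disagree only for p-values in a narrow band. This makes the right correction easy to identify. It does not remove the conflict: the text available states no order of precedence, and a reader of the protocol alone would apply 0.05. Some opening and signature pages were not available, so the absence of a precedence rule can be asserted only for the text that was.

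Second, protocol 11.1 gives 0.025 as an input to the power calculation, not as a test threshold. That is fair. The direct clash of decision rules is protocol 11.2 against SAP 8.2, and it stands without 11.1.

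Third, AVATAR v drugs is the only primary objective, so testing it alone at 0.05 would carry 5% error. That would be a workable design with a stated testing order, but neither document has one. It also departs from the multiplicity rationale in 11.1. The 9.1% figure therefore depends on treating the two comparisons as one family, as 11.1 does.

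Fourth, the power figure and the confidence-interval level are separate from the threshold conflict. This is correct. The power error is on the safe side, and reporting 95% intervals beside a 0.025 test is not in itself an error. The change-history entry for SAP 8.3 refers back to the primary-analysis edits, which suggests 0.025 may have been meant there too, but the section does not say so.

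**Conclusion.** The concern holds and must be fixed before analysis. Protocol 11.2 and SAP 8.2 set incompatible thresholds for the primary endpoint, and 0.025 is the value consistent with the stated correction and the two planned comparisons.

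The practical reach is limited but real. The result would depend on the document read in about 6% of trials for AVATAR v drugs and 7% for AVATAR v conventional if the design effects are true, and in at most about 11% for any true effect. Using 0.05 for both comparisons roughly doubles the family-wise error, from 4.6% to 9.1% at correlation 0.5 (from 4.9% to 9.8% at correlation 0, and from 4.3% to 8.3% at 0.7). These figures rest on the plan's event proportions, 100 evaluable patients per arm and normal approximations.

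Separately, the stated power of 0.80 for AVATAR v drugs is wrong for its own inputs. It is about 0.85 at two-sided 0.025. The value 0.80 fits the 0.017 that the SAP change history says was replaced, so it was probably carried over. The trial is not underpowered for this comparison as a result.

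**What to change.** - **Protocol 11.2:** replace 0.05 with two-sided 0.025 for each of the two primary-endpoint comparisons, matching SAP 8.2.
- **Other outcomes:** in the same edit, align protocol 11.2 with SAP 8.4 at 0.025 per comparison, and write that level into SAP 8.3. This covers the two comparisons within each endpoint. It does not control error across the three secondary endpoints, and the text should not imply that it does.
- **Protocol 11.1 and SAP 5.5:** restate power at two-sided 0.025 as about 0.85 for AVATAR v drugs (103 events) and about 0.79 for AVATAR v conventional (60 events).
- **Minor:** show 97.5% intervals in SAP Tables 4.3.1 and 4.3.2. With the 95% intervals now in the Table 4.3 shell, a result in the disputed zone could show an interval excluding 1 beside a non-significant test.

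The cost is text edits only, with no change in sample size. Relative to protocol 11.2 as written, power falls from 0.90 to 0.85 for AVATAR v drugs and from 0.86 to 0.79 for AVATAR v conventional. The first is above the planned 0.80 and the second is close to it.
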